##### **4.9.2 Analysis of Treatment Group Comparability**

Baseline characteristics will be reported by arm. Categorical variables will be summarized as frequency and proportion and continuous variables by mean and standard deviation or median and 25th and 75th percentiles, as appropriate based on normality.

##### **4.9.3 Efficacy Analysis**

###### **a. Primary Endpoint**

The proportion of patients with IRRs during or after the first infusion on day 0 will be reported for each arm. Cetirizine will be considered non-inferior to diphenhydramine if the lower limit of the two-sided, 90% confidence interval for the difference in proportions (diphenhydramine-cetirizine) is greater than the non-inferiority margin of -0.30^5.

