## **2. OBJECTIVES**

### **2.1 PRIMARY OBJECTIVE**

The primary objective of this pilot study is to evaluate whether there is some evidence that cetirizine is non-inferior to diphenhydramine in limiting the proportion and severity of reactions from OCR infusions.

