## **3. STUDY DESIGN**

### **3.1 DESCRIPTION OF THE STUDY**

This 6-month randomized controlled pilot study will determine whether there is some evidence that cetirizine is better tolerated than diphenhydramine without an increase in IRRs. Fifty-two patients, 26 patients per arm, will be randomized in a 1:1 ratio to receive cetirizine or diphenhydramine as premedication prior to OCR infusions on day 0 (1st half dose of 300mg), day 14 (2nd half dose of 300mg) and week 24 (1st full dose of 600mg). Neurological exams and the estimated Expanded Disability Status Scale (EDSS) will be obtained at screening and week 24, as well as premature termination visits, if applicable. Stanford Sleepiness Scale (SSS), and the Visual Analog Scale – Fatigue (VAS-F) will be administered at screening, baseline, day 14, and week 24. Modified Fatigue Impact Scale (MFIS) and Multiple Sclerosis Impact Scale (MSIS-29) will be administered at screening and week 24. MSIS-29 and MFIS will also be administered at premature termination, if applicable. Treatment Satisfaction Questionnaire for Medication (TSQM) will be administered at baseline, day 14, and week 24. TSQM, SSS, and VAS-F will be administered within 2 hours after each OCR infusion, followed by a phone call on the next business day following each infusion to collect and assess infusion reactions or other AEs.

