#### **4.9 STATISTICAL METHODS**

##### **4.9.1 Analysis of the Conduct of the Study**

For the primary, non-inferiority endpoint, analysis will be on both the intention-to-treat and per-protocol populations (two-sample proportion non-inferiority test). Analysis for secondary endpoints will be on the intention-to-treat population. The intention-to-treat population is defined as all randomized patients, and the per-protocol population will be those who completed the study as per protocol specification.

If the study is terminated before planned enrollment is reached, only descriptive analysis will be performed.

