#### **4.9.6 Determination of Sample Size**

Based on the results of the OPERA I and II trials, we assume that 25% of patients in the diphenhydramine arm and 25% of patients in the cetirizine arm will experience mild to severe IRRs during or after receiving the first infusion on day 0. Assuming that a 30% absolute difference (i.e. margin = - 0.30) in the proportion of patients with IRRs between premedication groups is the maximum relevant difference when holding that cetirizine is not inferior to diphenhydramine, 26 patients per arm are needed to achieve 80% power with a one-sided significance level of 0.05. As this is a pilot study, we allow a large margin to establish some evidence of non-inferiority. The two-sample proportion test for non-inferiority in the R package Trial Size was used for the calculation.

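### Does the non-inferiority verdict in section 4.9.3a claim more than a pass on the -0.30 margin can support?

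*Combined protocol and SAP*

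**What the plan says.** The primary endpoint is the proportion of patients with an IRR at the day 0 infusion (section 3.3.1). Section 4.9.3a has each arm's proportion reported and then gives the rule: "Cetirizine will be considered non-inferior to diphenhydramine if the lower limit of the two-sided, 90% confidence interval" for the difference, diphenhydramine minus cetirizine, "is greater than the non-inferiority margin of -0.30". Section 4.9.1 applies it to two analysis sets: "For the primary, non-inferiority endpoint, analysis will be on both the intention-to-treat and per-protocol populations".

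The sample size in section 4.9.6 rests on equal rates: "we assume that 25% of patients in the diphenhydramine arm and 25% of patients in the cetirizine arm" have an IRR on day 0. It takes as an assumption that a 30-point absolute difference "is the maximum relevant difference when holding that cetirizine is not inferior to diphenhydramine", and closes with the reason for its size: "As this is a pilot study, we allow a large margin to establish some evidence of non-inferiority".

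The aims carry the same limit. Section 2.1 sets out to "evaluate whether there is some evidence that cetirizine is non-inferior to diphenhydramine". Section 3.1 says the study "will determine whether there is some evidence that cetirizine is better tolerated than diphenhydramine without an increase in IRRs".

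**The concern.** Three features together suggest that the plan could overstate its result.

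- **The verdict is unqualified.** The sentence in 4.9.3a that a report will apply does not repeat the pilot caveat found in 2.1, 3.1 and 4.9.6.
- **The margin is wide.** Thirty points is more than the assumed control rate. Section 4.9.6 also describes it in two ways, as the largest difference that matters and as a generous allowance for a pilot.
- **The aim sounds stricter than the rule.** Section 3.1 speaks of no increase in IRRs, whereas a pass guarantees only that an excess of 30 points or more is excluded.

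A reader who saw only the verdict might conclude that cetirizine does not raise the IRR rate. Section 3.2 says there is no evidence yet that newer antihistamines are as effective at limiting reactions, so a pass could be taken as filling that gap. The plan also does not expressly commit to reporting the difference with its interval.

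**Working it through.** **Inputs.** Rates of 25% in both arms, margin 0.30, one-sided 0.05, 80% power and 26 per arm (4.9.6). Two-sided 90% interval with lower limit above -0.30 (4.9.3a).

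**1. The plan's own figure.** With the unpooled normal approximation,

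n per arm = (1.6449 + 0.8416)² × 2 × 0.25 × 0.75 / 0.30² = 6.1827 × 0.375 / 0.09 = 25.76, rounded up to 26.

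The standard error at 26 per arm is √(0.375/26) = 0.1201. Power is Φ(0.30/0.1201 − 1.6449) = Φ(0.853) = 80.3%. The lower limit of a two-sided 90% interval corresponds to a one-sided 5% test, so the size, interval and significance level agree.

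**2. What the margin means.** 0.25 + 0.30 = 0.55, which is 2.2 times the assumed control rate.

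**3. Chance of a pass.** This comes from exact binomial enumeration of all outcomes with 26 per arm and a true diphenhydramine rate of 25%. Section 4.9.3a names no interval method, so two are shown.

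| True cetirizine rate | Wald | Newcombe |
|---|---|---|
| 25% | 0.820 | 0.820 |
| 30% | 0.670 | 0.672 |
| 35% | 0.499 | 0.504 |
| 40% | 0.335 | 0.345 |
| 50% | 0.106 | 0.120 |
| 55% | 0.049 | 0.060 |

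The rule is close to its nominal 5% at the boundary and rejects a true doubling nearly nine times in ten. It cannot reliably detect a 10-point rise.

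**4. What a pass excludes.** With equal true rates of 25%, the mean lower limit among passing results is -0.154 by either method, so a pass typically excludes more than the guaranteed minimum. Even so, 73% of passes leave an excess of 10 points or more open, and 35 to 37% leave 20 points or more open. The lower limit is above zero in 5.1% of trials.

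**5. Examples (diphenhydramine vs cetirizine).**

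- 6/26 vs 6/26: lower limit -0.192 (Wald), -0.190 (Newcombe); passes.
- 6/26 vs 8/26: difference -0.077, Wald standard error √(0.006827 + 0.008193) = 0.1226, lower limit -0.077 − 1.6449 × 0.1226 = -0.279 (Newcombe -0.270); passes.
- 6/26 vs 9/26: -0.320 (Wald), -0.309 (Newcombe); fails.

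With 5 to 9 diphenhydramine events, the largest observed excess that passes is two patients, or 2/26 = 7.7 points.

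**6. What rewording would move.** Every figure above is fixed by the sample size, the margin and the interval. Different wording in 4.9.3a changes none of them.

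**The case for a change.** The best case for a change is that the decision sentence is the one people quote, and that settling its meaning in advance costs a line of text. The caveat of some evidence describes the strength of the evidence; it does not turn no increase into no increase of 30 points or more. Calling 30 points the largest difference that matters sits awkwardly beside calling it a large pilot margin. Nothing expressly promises that the interval will be published.

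Some of this stands. Section 4.9.3a does omit the caveat, the reporting of the interval is left implicit, and a pass is compatible with a real increase. The rest is weaker.

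- Non-inferiority always means relative to a stated margin, and 4.9.3a states its margin in the verdict sentence.
- No non-inferiority test excludes every increase. The 5% of trials with a lower limit above zero is simply the one-sided error rate when true rates are equal, and would be about that at any margin.
- The two descriptions in 4.9.6 can be read together: the first is a working assumption for the calculation, and the second explains why it was set so wide.
- The interval must be computed to reach the verdict, and each arm's proportion will be reported, so with about 26 per arm a reader can reconstruct it approximately.
- Writing the 30-point threshold into the aims would introduce errors. Section 3.1 covers three infusions, but the margin applies only to day 0; day 14 and week 24 are compared by Fisher's exact tests with no margin (4.9.3b). Section 2.1 covers severity as well as proportion, and severity is not tested against -0.30.

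**Conclusion.** The concern does not call for a change. The plan's text and the figures behind the concern check out, but they describe the accepted limits of a 52-patient pilot with an openly wide margin. A sponsor following the plan as written would reach a sound conclusion: some evidence of non-inferiority on day 0, relative to -0.30. Trading precision for feasibility is fair here because the plan says that it does so.

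What is left is reporting detail that analysts would normally supply: the difference with its 90% interval, and the pilot caveat repeated beside the verdict. It would help a reader but has no effect on the design or analysis.

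The quoted pass probabilities assume a true diphenhydramine rate of 25%, complete day 0 data on 26 patients per arm, and a Wald or Newcombe interval. The two methods differ by no more than about 1.4 percentage points at the rates tabulated.

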### **b. Secondary Endpoints**

The proportion of patients with IRRs during or after infusion will be compared using Fisher's exact tests at day 14 and week 24, as we expect the proportion of IRRs to be small at these time points based on OPERA I and II. Additionally, the proportion of IRRs after each infusion will be plotted overall and by severity for the two arms. At day 0, day 14, and week 24, TSQM scores will be compared between arms using Wilcoxon Rank Sum or two-sample t-tests, as appropriate based on normality, and SSS and VAS-F scores will be compared using Wilcoxon rank sum tests. MFIS, physical MSIS-29, and psychological MSIS-29 will be compared at week 24 using multiple linear regression with analysis of covariance (ANCOVA), adjusting for the screening score.

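### Fisher's exact test for the day-14 and week-24 IRR comparisons is valid but conservative; Boschloo's exact test keeps an assumed two-sided 5% level and never has less power

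*Combined protocol and SAP*

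**What the plan says.** Section 4.9.3b states that the proportions of patients with an IRR "will be compared using Fisher's exact tests at day 14 and week 24". It gives the reason: "as we expect the proportion of IRRs to be small at these time points based on OPERA I and II". It names no significance level, sidedness, expected rate or target difference for these comparisons.

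Section 3.1 sets the size: "Fifty-two patients, 26 patients per arm, will be randomized in a 1:1 ratio". Section 4.9.6 derives that number for the day-0 primary endpoint only, at a one-sided 0.05 level. Under 4.9.1, "Analysis for secondary endpoints will be on the intention-to-treat population". The Premature Termination Visit text in 4.5.1 says that withdrawn patients are not replaced, and 4.9.5 describes imputation for the primary endpoint only.

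**The concern.** Few expected events are a good reason to use an exact test. They are also the condition in which Fisher's conditional test is furthest below its nominal level, because few tables can reach p ≤ 0.05. At 26 per arm, 0 events against 5 is not significant by Fisher's test (p = 0.051).

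The non-inferiority criterion covers day 0 only. At day 14 and week 24 these are the only planned between-arm tests of IRR proportions; the rest is a plot. Section 3.1 asks whether cetirizine is better tolerated without more IRRs, so a missed increase at a later infusion would be reported as no significant difference, which favours cetirizine. If another exact test has the same guaranteed level and rejects more tables, the power lost with Fisher's test is given up for nothing.

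**Working it through.** **Inputs from the documents.** 26 per arm (3.1, 4.9.6); Fisher's exact test at day 14 and week 24 (4.9.3b).

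**Assumptions.** Two-sided 5% level. The documents give no later-infusion IRR rates, so a lower-arm rate of 2% to 10% is used for power and a common rate of 5% to 15% for size.

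**The plan's own figure.** With 25% in each arm, margin 0.30, one-sided 0.05 and 80% power:

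n = (1.645 + 0.842)² × (2 × 0.25 × 0.75) / 0.30² = 6.18 × 0.375 / 0.09 = 25.76, rounded up to 26.

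This agrees with 4.9.6. It says nothing about power at the later infusions.

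**Method.** All 27 × 27 = 729 possible tables were enumerated under two independent binomials. For a rejection region R,

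P(reject) = Σ over (a, b) in R of Bin(a; 26, p1) × Bin(b; 26, p2).

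Size is this sum with p1 = p2, and power is the sum with p1 ≠ p2. Fisher's region is every table with two-sided Fisher p ≤ 0.05. Boschloo's test uses the two-sided Fisher p as its statistic and takes the largest cutoff whose size, maximised over the common rate, is at most 0.05. At 26/26 that cutoff is 0.0828. Since 0.0828 exceeds 0.05, Boschloo's region contains Fisher's.

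**One table by hand.** For 0/26 vs 5/26, one tail is C(26,5)/C(52,5) = 65,780/2,598,960 = 0.0253. Doubling gives Fisher p = 0.0506. Boschloo p is 0.0322.

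**Size at 26/26.**

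| Common rate | Fisher | Boschloo |
|---|---|---|
| 5% | 0.10% | 0.47% |
| 10% | 0.99% | 2.05% |
| 15% | 2.01% | 3.25% |
| Maximum over all rates | 2.80% | 4.84% |

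Fisher's test rejects 394 tables. Boschloo's rejects those plus 30 others (424), for example 0 vs 5, 2 vs 8 and 3 vs 10.

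**Power at 26/26.**

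| Rates | Fisher | Boschloo | Gain (points) |
|---|---|---|---|
| 5% vs 15% | 8.1% | 13.0% | 4.9 |
| 5% vs 20% | 21.7% | 28.7% | 7.0 |
| 5% vs 25% | 39.7% | 47.5% | 7.8 |
| 5% vs 30% | 57.7% | 65.3% | 7.6 |
| 10% vs 20% | 9.2% | 12.9% | 3.6 |
| 10% vs 30% | 32.2% | 40.8% | 8.6 |
| 10% vs 35% | 46.9% | 56.9% | 10.0 |
| 10% vs 40% | 61.6% | 71.5% | 9.8 |

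**Gain at other observed arm sizes (points).**

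| Arm sizes | 5% vs 15% | 5% vs 25% | 10% vs 40% |
|---|---|---|---|
| 25/25 | 4.8 | 7.9 | 9.9 |
| 24/24 | 0.3 | 2.5 | 6.2 |
| 26/24, smaller arm has the higher rate | 0.0 | 0.1 | 2.4 |
| 26/24, larger arm has the higher rate | 6.7 | 11.2 | 7.0 |
| 25/24, smaller arm has the higher rate | 5.8 | 4.4 | 6.0 |

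For 2% vs 15% the gain is 9.9 points at 26/26, about 0.1 at 24/24 and 23/23, 0.0 at 26/24 (smaller arm higher) and 12.6 at 25/24 (smaller arm higher). No Fisher rejection was lost at any arm sizes tried, so no gain was negative.

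**The case against.** Fisher's test is a conventional, valid choice for sparse 2×2 tables. It controls its level, the plan gives its reason, and these are secondary comparisons in a pilot sized for another endpoint. That stands, and it is why the point is an optional efficiency gain.

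The size of the benefit is also uncertain, and this stands too. The gains near 10 points from a 10% base need a rate of 35% or 40% in the worse arm. That is above the 25% assumed for day 0, while the plan expects small rates later. The gain depends on the exact arm sizes and can vanish with two losses in one arm. Fisher's maximum of 2.8% is likewise specific to 26/26: it is 3.8% at 26/25 and 4.4% at 25/24.

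A reader might infer a general gain of 8 to 10 points. The documents do not support that: they give no later-infusion rates and no assurance of 26 observed per arm. A reader might also infer that the change would let the trial exclude an increase in IRRs at later infusions. It would not. A non-significant difference test does not show absence of an increase, whichever test is used.

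What does not stand is that the choice is neutral. Boschloo's region contains Fisher's, so the substitute cannot do worse at any rate or arm size, and its level is still guaranteed.

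**Conclusion.** The point holds as a free improvement. With a two-sided 5% level and 26 observed per arm, Fisher's test runs at about 0.1% to 2.0% for common rates of 5% to 15%, and never above 2.8%. Boschloo's test stays within 5% (maximum 4.8%). It adds about 4 to 10 points of power for rises of 10 to 30 points from a 5-10% rate. At other arm sizes the gain is about 0 to 13 points and never negative.

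The level, the sidedness and the event rates are assumptions, since the plan states none of them for these tests. The change reduces the conservatism without removing it: Boschloo's size is still about 0.5% at a 5% rate. Power stays modest, for example 47.5% for 5% vs 25%. It would be wrong to read this as an error in the plan, because Fisher's test keeps its level.

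**What to change.** In 4.9.3b, replace Fisher's exact test with Boschloo's exact test for the day-14 and week-24 IRR comparisons, prespecified as two-sided at 5%. State that the statistic is the two-sided Fisher p-value, because the guarantee of never losing a Fisher rejection rests on that. At 26/26, a version built from two one-sided 2.5% Boschloo tests gives the same rejection region.

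The cost is one phrase, settled before the data are analysed. It needs no extra patients or data, and the test is available in standard software. If the sponsor keeps Fisher's test, the level and sidedness should still be stated.

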### **3.2 RATIONALE FOR STUDY DESIGN**

Shortly after the approval of OCR, we followed the premedication protocol used in OPERA I and II which included 100mg of methylprednisolone, 1 gram of acetaminophen, and 50mg of IV diphenhydramine. However, many patients experienced extreme sedation which caused severe drowsiness and impaired their ability to function, drive, or work during and after the infusion, and even the following day. As a result, we have decreased the dose of diphenhydramine to 25mg administered either IV or orally which has resulted in less, but still marked, drowsiness. Newer antihistamines such as cetirizine may be better tolerated; however, there is no evidence that they will be as effective in minimizing infusion reactions.

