### **3.5 COMPLIANCE WITH LAWS AND REGULATIONS**

This study will be conducted in accordance with current ICH GCP Guidelines and the Code of Federal Regulations for clinical research, applicable national and local health authorities, and IRB requirements. Any amendment to the study protocol must be approved by Providence IRB before implementation. AEs and protocol deviations must be reported according to the guideline of the IRB.

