#### **4.3. STUDY TREATMENT**

Patients will be enrolled and randomized to either the diphenhydramine or the cetirizine arm to be administered before their OCR doses, after informed consent and screening assessment have been completed. The premedication and OCR will be paid for by the patient or by the patient's insurance. Patients may receive any generic products of cetirizine or diphenhydramine that are available at their infusion center and do not require the same brand of the premedication for their subsequent infusions. The same brand does not need to be used at each OCR infusion, per patient.

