##### **4.5.1 Assessments during Treatment**

###### **Visit 1 or Screening Visit (-28 to -1 days prior to Baseline)**

- Informed consent
- Eligibility review
- Demographic information
- Review of disease and medical history
- Review of prior and concomitant medications, including lifetime MS disease modifying therapy history
- Reason(s) for switching to OCR
- Vital signs (blood pressure, heart rate, oral temperature, weight, and height)
- Neurological exam (may be historical exam if completed within 28 days prior to consent)
- Confirmation of estimated EDSS of 0 to 6.5, inclusive
- Laboratory assessments:
  - Urine or serum pregnancy test (females of childbearing potential only)
  - CBC and LFTs (may be historical laboratories if completed within 28 days prior to consent)
  - Hepatitis B testing (may be historical laboratories if completed within 6 months prior to consent)

- Serum immunoglobulins, quantitative (may be historical laboratories if completed within 28 days prior to consent)
- SSS
- VAS-F
- MFIS
- MSIS-29
- Adverse events

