#### **Visit 2 or Baseline Visit (Day 0)**

- Concomitant medications and adverse events
- Eligibility review (can be done day -7 to day 0)
- Randomization for premedication arm (can be done day -7 to day 0)
- Administration of premedication and OCR (300mg)
- Infusion reaction assessment
- TSMQ (Administered within 2 hours after OCR infusion, may be completed via phone)
- SSS (Administered within 2 hours after OCR infusion, may be completed via phone)
- VAS-F (Administered within 2 hours after OCR infusion, may be completed via phone)
- Phone Call (next business day) to assess infusion reactions and any other AEs

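### The SSS and VAS-F comparisons ignore the screening scores the trial already collects; a rank-based adjustment would add precision at almost no cost if those scores correlate with the outcome.

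*Combined protocol and SAP*

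**What the plan says.** Section 4.9.3b gives the method for the two scales: "SSS and VAS-F scores will be compared using Wilcoxon rank sum tests", at day 0, day 14 and week 24. No covariate is named. The next sentence of that section compares MFIS and the two MSIS-29 scores at week 24 "using multiple linear regression with analysis of covariance (ANCOVA), adjusting for the screening score".

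Section 3.1, the Visit 1 list in section 4.5.1 and the flowchart in Appendix A all schedule SSS and VAS-F at screening, on days -28 to -1. Section 4.3 places randomization "after informed consent and screening assessment have been completed", so the screening scores precede allocation. The day 0, day 14 and week 24 scores are taken within two hours after the infusion. The day 0 score is therefore an outcome, and screening is the only pre-treatment measurement of either scale.

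No stated efficacy analysis uses the screening SSS or VAS-F, and the plan does not explain why these scales are handled differently from MFIS and MSIS-29.

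**The concern.** When an outcome is also measured before randomization, adjusting for that measurement usually sharpens the treatment comparison, because it removes between-patient variation that the antihistamine did not cause. The plan applies this to MFIS over a gap of roughly 22 to 30 weeks. It does not apply it to VAS-F, also a fatigue scale, where the gap to day 0 is at most 28 days.

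The two endpoints matter to the reason for the trial. Section 3.2 reports that lowering the diphenhydramine dose still left a problem, "which has resulted in less, but still marked, drowsiness", and section 3.1 asks whether cetirizine is better tolerated. The formal secondary objective in section 2.2 is treatment satisfaction, however, and the trial is sized only for infusion reactions.

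With at most 26 patients per arm and no replacement of withdrawals, precision is scarce. No stratification is described, and the standard error of a baseline mean difference is sqrt(2/26) = 0.28 SD, so an imbalance larger than that arises by chance in about a third of such trials. A pre-specified adjustment deals with such an imbalance without a post hoc decision.

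**Working it through.** **The plan's own figure.** Section 4.9.6 assumes 25% reactions in each arm, a margin of 0.30, one-sided 0.05 and 80% power. The usual formula gives n = (1.645 + 0.842)² × 2 × 0.25 × 0.75 / 0.30² = 25.8, so 26 per arm, with 80.3% power at 26. The figure reproduces. It concerns the primary endpoint only and is not affected by this point.

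**Inputs for SSS and VAS-F.** From the documents: 26 per arm, 1:1 allocation, intention-to-treat for secondary endpoints. Not in the documents, and therefore assumed: two-sided 0.05, an effect of 0.6 SD, and a correlation r from 0 to 0.7.

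**Variance reduction.** On the rank scale under bivariate normality, adjustment multiplies the variance by 1 - rs², with rs = (6/π) asin(r/2). The equivalent unadjusted sample size is 26 / (1 - rs²).

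| r | rs² | equivalent n per arm |
|---|---|---|
| 0 | 0% | 26.0 |
| 0.2 | 3.7% | 27.0 |
| 0.3 | 8.3% | 28.3 |
| 0.5 | 23.3% | 33.9 |
| 0.7 | 46.6% | 48.7 |

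**Cost of adjusting.** With N = 52, estimating one covariate inflates the variance by about 1 + 1/(N - 4) = 1 + 1/48, or 2%. In linear-model terms, break-even is at (1 - r²)(49/48) = 1, so r² = 1/49 and |r| is about 0.14.

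**Simulated power per time point** (40,000 trials per cell, 0.6 SD). The Wilcoxon test uses the tie-corrected normal approximation. Rank ANCOVA regresses the overall rank of the outcome on arm and the overall rank of the screening score, with t on 2n - 3 degrees of freedom.

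| r | Wilcoxon, continuous | Rank ANCOVA, continuous | Wilcoxon, 7 categories | Rank ANCOVA, 7 categories |
|---|---|---|---|---|
| 0 | 54% | 54% | 51-53% | 52-53% |
| 0.2 | 54% | 55% | 51-53% | 53-54% |
| 0.3 | 54% | 57% | 51-53% | 54-56% |
| 0.5 | 54% | 65% | 51-53% | 61-63% |
| 0.7 | 54% | 79% | 51-53% | 74-77% |

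The seven-category score is an assumed form; the ranges cover even and skewed cut-points. The gain is about 0, 1, 3, 9-11 and 22-26 percentage points. With no true effect, rejection was 4.6% to 5.3% for both methods.

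**Sensitivity to the assumptions (continuous score).**

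- 0.4 SD: Wilcoxon 28%; rank ANCOVA 34% at r = 0.5 and 45% at r = 0.7.
- 0.8 SD: Wilcoxon 78%; rank ANCOVA 88% and 96%.
- 22 per arm left at week 24 (assumed), 0.6 SD: Wilcoxon 47%; rank ANCOVA 57% and 72%.
- A separate simulation at 0.7 SD (6,000 trials per cell, continuous and seven-level scores) gave gains of about 3, 10-11 and 21-22 points at r = 0.3, 0.5 and 0.7.
- If half or more of the patients sit in the lowest screening category (50% or 70% assumed), the gain falls to about 6-7 points at r = 0.5 and 13-19 at r = 0.7.

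**How old the covariate is.** Screening is 1 to 28 days before day 0. Week 24 is day 168 ± 14, so the gap to week 24 runs from 154 + 1 = 155 days to 182 + 28 = 210 days, about 22 to 30 weeks.

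**The case against.** The strongest reply is that nothing here is an error. The Wilcoxon test is valid under randomization, the endpoints are secondary, and the trial is a pilot. All of that stands, and it sets the weight of the point.

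The benefit also depends on a correlation nobody has reported. It could be low: screening is an untreated reading taken on another day, whereas the outcome follows an antihistamine, methylprednisolone and ocrelizumab within hours. At r of 0.3 or less the gain is about 3 points at most. This stands too, but it argues against expecting much rather than against adjusting, because almost nothing is lost at r = 0.

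The contrast with MFIS and MSIS-29 is not exact. Those scales carry no post-infusion timing rule, so their screening score is closer to a true baseline. That could justify a different method, but the plan does not say so.

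Finally, a rank-regression coefficient is hard to read on the SSS or VAS-F scale, and a rule is needed for a missing screening score. No blinding is described, so it may be hard to show that the change preceded sight of arm-level data. These are matters for the wording and dating of the amendment. They do not remove the advantage.

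**Conclusion.** The concern holds as a modest efficiency point. The plan leaves a pre-randomization measurement of each scale out of its efficacy analysis while adjusting the neighbouring endpoints for theirs, and gives no reason. Validity, the primary endpoint and the sample size are untouched.

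The size depends on r, which the documents do not give. At 26 per arm and an assumed 0.6 SD effect, the gain runs from nothing at r = 0 to about 10 points at r = 0.5 and 22 to 26 points at r = 0.7, less if screening scores bunch at the floor. At r of 0.2 or below it is negligible. Any benefit is more plausible at day 0 and day 14 than at week 24, where the screening score is months old. The point does not extend to TSQM, which has no screening score.

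**What to change.** Before arm-level data are examined, amend section 4.9.3b along these lines: at day 0, day 14 and week 24, SSS and VAS-F will be compared between arms by rank ANCOVA adjusting for the screening score, with unadjusted Wilcoxon rank sum tests reported as sensitivity analyses. Define rank ANCOVA as the regression of the overall rank of the post-infusion score on arm and the overall rank of the screening score.

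Add a clause on handling a missing screening score by a rule that ignores arm, so that the intention-to-treat population is kept, and report arm medians so that the result can be read on the original scale. Because screening may run to day -1 and randomization may take place from day -7, confirm that each screening score was completed before allocation. If the sponsor prefers the unadjusted test as the main analysis, one sentence giving the reason would also settle the point.

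The cost is a few lines of analysis wording, one degree of freedom per model and no new data. Section 3.5 also applies: "Any amendment to the study protocol must be approved by Providence IRB before implementation".
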